### **9.4.1. Serious Adverse Events**

In the interest of subject safety, and in order to fulfill regulatory requirements, all SAEs (regardless of their relationship to Study Drug) should be reported to the Sponsor or designee within 24 hours of the Study Center's first knowledge of the event. The collection of SAEs will begin after the subject signs the informed consent form and stop at the end of the subject's Follow-up Period which is defined as the last study visit (Visit 11). When the Investigator is reporting by telephone, it is important to speak to someone in person versus leaving a message. SAEs should be reported using an electronic SAE submission form whenever possible. In situations where the electronic SAE submission is unavailable, an Initial SAE Form should be completed and a copy should be faxed or emailed to the Sponsor or designee. The SAE reporting instruction, including the fax number and email address can be found in the Investigator site file for the study.

Detailed information should be actively sought and included as Follow-Up as soon as additional information becomes available. All SAEs will be followed until resolution. Serious Adverse Events that remain ongoing past the subject's last protocol-specified follow-up visit will be evaluated by the Investigator and Sponsor. If the Investigator and Sponsor agree the subject's condition is unlikely to resolve, the Investigator and Sponsor will determine the follow-up requirement.

### **9.4.2. Non-Serious Adverse Events**

The recording of non-serious AEs will begin after the subject signs the informed consent form and will stop at the end of the subject's Follow-up Period, which is defined as Visit 11. The Investigator will monitor each subject closely and record all observed or volunteered AEs on the Adverse Event Case Report Form.

### **9.4.3. Evaluation of Adverse Events (Serious and Non-Serious)**

The Investigator's opinion of the following should be documented on the Adverse Event Case Report Form.

#### 9.4.3.1. Relationship to the Study Drug

The event's relationship to the Study Drug (ION-827359 or placebo) is characterized by 1 of the following:

- **Related:** There is clear evidence that the event is related to the use of Study Drug, e.g., confirmation by positive re-challenge test
- **Possible:** The event cannot be explained by the subject's medical condition, concomitant therapy, or other causes, and there is a plausible temporal relationship between the event and Study Drug (ION-827359 or placebo) administration
- **Unlikely/Remote:** An event for which an alternative explanation is more likely (e.g., concomitant medications or ongoing medical conditions) or the temporal relationship to Study Drug (ION-827359 or placebo) administration and/or exposure suggests that a causal relationship is unlikely (For reporting purposes, Unlikely/Remote will be grouped together with Not Related)
- **Not Related:** The event can be readily explained by the subject's underlying medical condition, concomitant therapy, or other causes, and therefore, the Investigator believes no relationship exists between the event and Study Drug

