### 9.3.2. Adverse Drug Reaction and Suspected Unexpected Adverse Drug Reaction

#### Adverse Drug Reaction (ADR)

In the *pre-approval* clinical experience with a new medicinal product or its new usages, particularly as the therapeutic dose(s) may not have been established, ADR is defined as follows:

All noxious and unintended responses to a medicinal product related to any dose should be considered adverse drug reactions.

The phrase "responses to a medicinal product" means that a causal relationship between the medicinal product and the AE has been determined by the Sponsor as at least a reasonable possibility, i.e., the relationship cannot be ruled out.

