#### **10.6.2. Safety Analysis**

Treatment duration and amount of Study Drug (ION-827359 or placebo) received will be summarized by treatment group.

All treatment emergent AEs, all treatment emergent AEs potentially related to Study Drug, all treatment emergent serious AEs, and all treatment emergent serious AEs potentially related to

Study Drug (ION-827359 or placebo) will be summarized for each treatment group using the Medical Dictionary for Regulatory Activities (MedDRA™) coding system, by system organ class, preferred term, relationship to Study Drug, and severity. Narratives of deaths, SAEs, including early withdrawals from treatment and from study due to AE, will also be provided.

Laboratory tests to ensure subject safety including chemistry panel, complete blood count with differential, coagulation panel, etc., will be summarized by study visits for each treatment group. These safety variables will also be presented as change and percent change from Baseline over time after Study Drug administration, as appropriate.

Vital sign and ECG measures will be tabulated by treatment group. In addition, the number of patients who experience abnormalities in clinical laboratory evaluations will be summarized by treatment group.

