### **3.4.2 Adverse Events**

An adverse event will be regarded as treatment emergent if it is present prior to receiving the first dose of study drug and subsequently worsens, or is not present prior to receiving the first dose of study drug but subsequently appears.

In addition, if the severity of an AE changes during the study, a separate AE will be recorded for each severity on the AE CRF. The “first” and “second” AE records will be identified based on the AE start date. AE start date of the second record will be the AE stop date of first record. These linked events should be compared pairwise. Consider the following two cases,

where the AE severity (mild/moderate/severe) and seriousness (Yes/No) between the two records in a pair are compared.

Case 1: The first AE record in the pair occurs before the first dosing, and the second AE record occurs after the first dosing.

If the AE severity or seriousness of the second record is worse than that of the first record, then only the second AE is deemed as a TEAE. Otherwise, neither record is considered as TEAE.

Case 2: Both AE records in the pair occur after first dosing.

The worst AE is considered as a TEAE.

The most conservative approach will be used to determine if the event occurs after the treatment. For example, if the onset date or resolution date of an AE is prior to the first study treatment date, it will be considered to have occurred prior to the study period. If the onset or resolution date of an AE is a partial date with only month or year available or complete missing, then the event is assumed to be within the study period unless the year is prior to the year of the first study treatment date, or if in the same year, the month is prior to the month of the first study treatment date.

The incidence of AEs will be summarized by Medical Dictionary for Regulatory Activities (MedDRA) preferred term and system organ class for:

- Any treatment emergent adverse events
- Related treatment emergent adverse events. Related is defined as “Related”, “Possible”, or missing relationship to study drug
- Any treatment emergent adverse events by severity. At each level of patient summarization, a patient is classified according to the highest severity if the patient reported one or more events. Adverse events with missing severity will categorized as “Missing” for this summary
- Related treatment emergent adverse events by severity
- Serious treatment emergent adverse events

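### The *Possible* causality category is stricter than the protocol's own adverse-reaction standard and leaves a gap before *Unlikely/Remote*, so related-TEAE counts for airway events may be too low

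*Combined protocol and SAP*

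**What the plan says.** Protocol 9.4.3.1 gives the investigator four ratings.

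- *Related* needs clear proof of a link; a positive re-challenge is the example given.
- *Possible* is worded as follows: "The event cannot be explained by the subject's medical condition, concomitant therapy, or other causes, and there is a plausible temporal relationship" with dosing. Both parts are required.
- *Unlikely/Remote* has two routes. The first is worded: "An event for which an alternative explanation is more likely (e.g., concomitant medications or ongoing medical conditions". The second is timing or exposure that argues against a causal link.
- *Not Related* has two parts. The first is worded: "The event can be readily explained by the subject's underlying medical condition, concomitant therapy, or other causes". The second is that the investigator sees no link to Study Drug.

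On how the third rating is reported, the section adds: "For reporting purposes, Unlikely/Remote will be grouped together with Not Related".

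Protocol 9.3.2 describes an adverse drug reaction differently. There the sponsor must have judged the causal relationship "as at least a reasonable possibility, i.e., the relationship cannot be ruled out". Section 9.2 also uses a reasonable-possibility test when the sponsor assesses serious events.

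Protocol 10.6.2 promises, among the safety tables, "all treatment emergent AEs potentially related to Study Drug". SAP 3.4.2 implements this as "Related treatment emergent adverse events. Related is defined as" a rating of *Related*, *Possible* or missing. The same definition feeds the related-by-severity and the serious-and-related tables.

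**The concern.** A causality scale should give each event a place, and the boundary between related and not related should sit where the protocol says it sits. Here *Possible* asks the investigator to exclude other causes first, whereas 9.3.2 asks only whether the drug can be excluded.

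The difference matters most for airway events in this trial. Every patient has COPD with frequent cough and phlegm (5.1, 6.1.1), and section 2.1 lists chronic cough, sputum and dyspnoea as features of chronic bronchitis. The disease is thus a candidate explanation for many of the events that an inhaled drug might cause. Bronchospasm after inhalation is also the harm that Amendment 3 was written to prevent. At stake is whether the related-TEAE tables show airway reactions at the threshold that a reader of 9.3.2 and 10.6.2 would expect.

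**Working it through.** The plan states no figure on this point, so the check sets the definitions side by side.

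**Step 1: one test event.** Take a new or worsened airway event soon after inhalation, for which Study Drug and COPD are equally credible causes.

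| Rating (9.4.3.1) | Requirement | Met? |
|---|---|---|
| *Related* | Clear evidence, with re-challenge as an example | No: credible only |
| *Possible* | Plausible timing, and no explanation from the condition, other therapy or other causes | Timing yes; second part no |
| *Unlikely/Remote* | A more likely alternative, or timing or exposure against the drug | No: equally credible, and timing fits |
| *Not Related* | Readily explained otherwise, and no relationship believed to exist | First part arguable; second part no |

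The event meets none of the four.

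**Step 2: the same event under 9.3.2.** The drug cannot be excluded, so the event passes that standard.

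**Step 3: follow it into SAP 3.4.2.**

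| What the investigator enters | In the related tables? | Agrees with 9.3.2? |
|---|---|---|
| *Possible*, despite the wording | Yes | Yes |
| Left blank | Yes, missing counts as related | Yes |
| *Unlikely/Remote* | No | No |
| *Not Related* | No | No |

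Measured against 9.3.2, the related count is either right or too low. Once the field is completed, an error from this source can only lower it.

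**Step 4: can the size be fixed?** SAP 1.1 gives 59 patients dosed. At 2:2:1:1, and assuming the dosed patients follow that ratio, 59 × 4/6 = 39.3, or about 39 on active drug. Let *r* be the share of them with a drug-caused airway event and *m* the share of those events coded as unrelated. Both are assumed; the documents give neither. Patients left in the related table = 39 × *r* × (1 − *m*):

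| *r* | *m* = 0 | 25% | 50% | 90% |
|---|---|---|---|---|
| 10% | 3.90 | 2.93 | 1.95 | 0.39 |
| 20% | 7.80 | 5.85 | 3.90 | 0.78 |
| 30% | 11.70 | 8.78 | 5.85 | 1.17 |

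The result runs from no loss to almost total loss depending on *m*, which nothing in the documents fixes.

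**Step 5: what is untouched.** TEAEs of any cause are tabulated overall and by severity. SAP 3.3.1 tabulates FEV1 falls above 20%, by patient and by dose, with no causality judgement. That table is only a partial substitute. Appendix A schedules spirometry after Study Drug on Days 1 and 57, which is 2 of 13 doses (2/13 = 15%). Seven of the 13 doses are taken at home (6.1.3), and cough or dyspnoea without a 20% fall would not appear.

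**The case against.** The strongest reply is that the rating is the investigator's opinion (9.4.3). Symptoms already present are adverse events only if they worsen (9.4), and patients enter with COPD that has been stable for four weeks (5.1). An investigator can reasonably hold that stable COPD does not explain an acute event just after a dose, and code it *Possible*. This stands.

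A reader might infer something stronger: that virtually no airway event could be coded related, or that the related count would be near zero whatever the true rate. The documents do not support that. Step 1 shows that the ambiguous event fails *Unlikely/Remote* and *Not Related* too, so its coding is undetermined rather than forced. Re-challenge is only an example under *Related*, and weekly dosing gives some opportunity to see recurrence. That opportunity is limited: a patient who stops gives no re-challenge, and only 10 patients had completed Week 14 (SAP 3.3).

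A reader might also infer that 9.4.3.1 reverses a threshold set for the same judgement, or that non-serious events are never re-rated. Section 9.3.2 describes a sponsor determination and 9.4.3.1 an investigator rating, so assessor and purpose differ. The sponsor's separate causality assessment in 9.2 covers serious events, but the medical monitor reviews all adverse events (SAP 2.4.1). What can be said is that no re-rating procedure feeding the tables is described.

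Finally, in a placebo-controlled trial the comparison of all-causality events between arms is better evidence than individual attribution. This is true, and it limits the harm. It does not repair the related tables that the plan commits to produce.

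**Conclusion.** The point holds as a conflict of definitions with a known direction and an unknown size. *Possible* is stricter than the 9.3.2 standard and does not adjoin *Unlikely/Remote*. An airway event with plausible timing that either the drug or COPD could explain is literally barred from *Possible*. If it is then coded *Unlikely/Remote* or *Not Related*, it drops out of the related-TEAE tables.

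Related counts for respiratory events may therefore be biased downward. This rests on some investigators applying the wording literally; the documents give no way to say how many. Blinded investigators use the same wording for placebo patients, so counts in every arm may be affected. The all-causality tables and the FEV1-reduction table do not depend on it.

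**What to change.** In protocol 9.4.3.1, define *Possible* as plausible timing where a causal role of Study Drug cannot be excluded, even if the patient's condition, other therapy or another cause could also account for the event. Keep *Unlikely/Remote* for a more likely alternative or implausible timing. The two categories then adjoin, and the investigator scale matches 9.3.2.

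Redefinition cannot recode past events: treatment ended on 29 April 2021 and the SAP is dated 26 August 2021. For events already coded, amend SAP 3.4.2 to:

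- show *Unlikely/Remote* separately from *Not Related*;
- add a table of respiratory TEAEs by arm without regard to causality and, where onset times exist, by time since inhalation;
- present any table that counts *Unlikely/Remote* respiratory events as related only as a labelled sensitivity analysis. It would include events whose alternative cause was judged more likely, and would miss ambiguous events coded *Not Related*.

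The cost is one reworded definition and a little more table work. The downside is that more events will be classed as related.

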#### 9.4.3.2. Severity

The severity of AEs and SAEs relating to laboratory tests and AEs at the injection site will be graded based on criteria from the Toxicity Grading Scale for Healthy Adult and Adolescent Volunteers Enrolled in Preventive Vaccine Clinical Trials, Sept 2007 (refer to [Appendix D](#)). Any AE not listed in [Appendix D](#) will be graded as follows:

- **Mild:** The event is easily tolerated by the subject and does not affect the subject's usual daily activities
- **Moderate:** The event causes the subject more discomfort and interrupts the subject's usual daily activities
- **Severe:** The event is incapacitating and causes considerable interference with the subject's usual daily activities

The severity of AEs and SAEs relating to laboratory tests and AEs at the injection site will be graded based on criteria from the Common Terminology Criteria for Adverse Events (CTCAE) Version 5.0, November 2017 (refer to [Appendix D](#)). Any AE not listed in [Appendix D](#) will be graded as follows:

- **Mild:** The event is easily tolerated by the subject and does not affect the subject's usual daily activities
- **Moderate:** The event causes the subject more discomfort and interrupts the subject's usual daily activities
- **Severe:** The event is incapacitating and causes considerable interference with the subject's usual daily activities

If the event is an SAE, then all applicable seriousness criteria must be indicated (criteria listed in Section [9.3.3](#)).

#### 9.4.3.3. Action Taken with Study Drug

Action taken with Study Drug (ION-827359 or placebo) due to the event is characterized by 1 of the following:

- **None:** No changes were made to Study Drug (ION-827359 or placebo) administration and dose
- **Not Applicable:** SAE/AE was reported during Screening Period prior to Study Drug administration
- **Permanently Discontinued:** Study Drug was discontinued and not restarted
- **Temporarily Interrupted, Restarted – Same Dose:** Dosing and/or dosing frequency was temporarily interrupted/changed or delayed due to the AE and restarted at the same dose
- **Reduced Dose:** Dosing was reduced, temporarily interrupted or delayed due to the AE and restarted at the next lower dose or reduced dosing frequency

#### 9.4.3.4. Treatment Given for Adverse Event

Any treatment (e.g., medications or procedures) given for the AE should be recorded on the Adverse Event Case Report Form. Treatment should also be recorded on the concomitant treatment or ancillary procedures eCRF, as appropriate.

#### 9.4.3.5. Outcome of the Adverse Event

If the event is a non-serious AE, then the event's outcome is characterized by 1 of the following:

- **AE Persists:** Patient terminates from the trial and the AE continues
- **Recovered:** Patient recovered completely from the AE
- **Became Serious:** The event became serious (the date that the event became serious should be recorded as the Resolution Date of that AE and the Onset Date of the corresponding SAE)
- **Change in Severity (if applicable):** AE severity changed

If the event is an SAE, then the event's outcome is characterized by 1 of the following:

- **Ongoing:** SAE continuing
- **Persists (as non-serious AE):** Patient has not fully recovered but the event no longer meets serious criteria and should be captured as an AE on the non-serious AE eCRF (the SAE resolution date should be entered as the date of onset of that AE)
- **Recovered:** Patient recovered completely from the SAE (the date of recovery should be entered as the SAE resolution date)
- **Recovered with Sequelae:** The signs/symptoms of the reported SAE have improved but not completely resolved, and a new baseline for the subject is established since full recovery is not expected
- **Fatal:** Patient died (the date of death should be entered as the SAE resolution date)
- **Unknown:** The outcome of the reported SAE is not available, e.g., patient is lost to follow-up

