### 9.3.3. Serious Adverse Event (SAE)

A SAE is any AE that in the view of either the Investigator or Sponsor, meets any of the following criteria:

- Results in death
- Is life threatening: that is, poses an immediate risk of death at the time of the event  
An AE or suspected adverse reaction is considered "life-threatening" if, in the view of either the Investigator or Sponsor, its occurrence places the subject at immediate risk of death. It does not include an AE or suspected adverse reaction that, had it occurred in a more severe form, might have caused death
- Requires inpatient hospitalization or prolongation of existing hospitalization  
Hospitalization is defined as an admission of greater than 24 hours to a medical facility and does not always qualify as an AE
- Results in a persistent or significant incapacity or substantial disruption of the ability to conduct normal life functions
- Results in a congenital anomaly or birth defect in the offspring of the subject (whether the subject is male or female)
- Important medical events that may not result in death, are not life-threatening, or do not require hospitalization may also be considered serious when, based upon appropriate medical judgment, they may jeopardize the subject and may require medical or surgical intervention to prevent 1 of the outcomes listed in this definition. Examples of such medical events include allergic bronchospasm requiring intensive treatment in an emergency room or at home, blood dyscrasias or convulsions that do not result in inpatient hospitalization, or the development of drug dependency or drug abuse

The terms "severe" and "serious" are not synonymous. Severity refers to the intensity of an AE (e.g., rated as mild, moderate, or severe, or according to National Cancer Institute Common Terminology Criteria for Adverse Events [NCI CTCAE]; OR Toxicity Grading Scale for Healthy Adult and Adolescent Volunteers Enrolled in Preventive Vaccine Clinical Trials; the event itself may be of relatively minor medical significance (such as severe headache without any further findings).

Severity and seriousness need to be independently assessed for each AE recorded on the eCRF.

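### SAP 3.4.2 Case 2 keeps only the worst of two linked post-dose AE records as the TEAE, carries no relatedness over, and does not define worst when severity and seriousness disagree

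*Combined protocol and SAP*

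**What the plan says.** Two places create linked records for one event.

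- Protocol 9.4.3.5. When a non-serious AE becomes serious, the date of that change "should be recorded as the Resolution Date of that AE and the Onset Date of the corresponding SAE". When an SAE stops being serious but continues, "the SAE resolution date should be entered as the date of onset of that AE". The outcome list for non-serious AEs also includes "Change in Severity (if applicable): AE severity changed".
- SAP 3.4.2. It states that "if the severity of an AE changes during the study, a separate AE will be recorded for each severity on the AE CRF", and it links the records by date: "AE start date of the second record will be the AE stop date of first record. These linked events should be compared pairwise".

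SAP 3.4.2 then sets out two cases, "where the AE severity (mild/moderate/severe) and seriousness (Yes/No) between the two records in a pair are compared". In Case 1 the first record precedes the first dose, and the second counts as treatment-emergent only if it is worse. In Case 2 both records follow the first dose, and the whole rule is "The worst AE is considered as a TEAE".

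The AE incidence summaries listed in SAP 3.4.2 (any, related, by severity, related by severity, serious, serious and related) all cover TEAEs only. Related means a record coded Related or Possible, or one with the relationship missing. Records that are not treatment-emergent appear in the listing with a flag.

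**The concern.** The general definition at the start of SAP 3.4.2 makes an event treatment-emergent if it was absent before the first dose and appeared afterwards. In Case 2 both records describe such an event, yet one of them loses its status. What that record holds then disappears from the tables.

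Relatedness is the most exposed attribute, because it plays no part in the comparison. Worst is also judged on two scales that the protocol treats as separate: section 9.3.3 says "Severity and seriousness need to be independently assessed for each AE recorded on the eCRF". The SAP gives no order between them, so two programmers could produce different serious-TEAE tables from the same data.

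Compared with describing the whole event, the rule can drop an attribute but never add one, so any error makes the safety profile look cleaner. Under SAP 1.1 and 3.3, treatment stopped early after toxicology findings and a review of the accumulated data, only 10 patients had completed Week 14, and efficacy is purely descriptive. The safety tables therefore carry much of the report's weight.

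**Working it through.** The plan gives no figure for this rule, so there is none to reproduce. I checked it by enumeration, then worked out what one patient is worth in each group.

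**1. Possible linked pairs.** Give each record a severity (3 levels), seriousness (2) and relatedness (2): 3 × 2 × 2 = 12 record types and 12 × 12 = 144 ordered pairs. A split implies a change in severity or seriousness. Removing the 6 × 2 × 2 = 24 pairs equal on both leaves 144 − 24 = 120.

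**2. Pairs on which the two scales disagree.** One record is more severe and the other is serious. There are 3 pairs of unequal severities × 2 orders × 4 relatedness combinations = 24 discordant pairs. The other 120 − 24 = 96 have one record at least as bad on both scales.

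**3. Apply Case 2 under both possible rankings of worst, keeping one record.**

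| Attribute lost | Severity ranked first | Seriousness ranked first |
|---|---|---|
| Relatedness | 30 of 120 | 30 of 120 |
| Seriousness | 24 of 120 | 0 |
| Severity | 0 | 24 of 120 |
| At least one | 48 of 120 | 48 of 120 |

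Relatedness is lost in the one of four combinations where only the dropped record is related: 120/4 = 30. The 48 are the 24 discordant pairs plus 96/4 = 24 concordant pairs that lose relatedness. If relatedness is always equal on the two records, 60 patterns remain and only the 12 discordant ones lose anything. If each pair is collapsed to the highest severity, any seriousness and any relatedness, 0 of 120 lose anything. These count possible patterns. They are not expected frequencies.

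**4. Two examples.**
- Mild and Possible, then severe and Not Related. The severe record is kept, and the event is absent from every related-TEAE table.
- Severe and non-serious, linked to moderate and serious. Keeping the first removes the event from the serious tables. Keeping the second reports it as moderate.

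**5. Weight of one patient.** Inputs: 59 dosed (SAP 1.1) and 2:2:1:1 allocation (protocol 4.2), assumed to hold among those dosed.
- Pooled active: 59 × 4/6 = 39.3, and 1/39.3 = 2.5 points.
- One dose group, or pooled placebo: 59 × 2/6 = 19.7, and 1/19.7 = 5.1 points.

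**The case against.** Several arguments limit the point.

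- **Case 1 uses the word only and Case 2 does not.** Exclusion of the other record is therefore not stated outright. It is still the natural reading: both records already qualify under the general definition, so the Case 2 sentence would otherwise do nothing.
- **Discordant pairs are uncommon.** They need an event to become serious while its severity falls, or to stop being serious while its severity rises. In ordinary worsening the worst record holds both attributes. This stands: the severity and seriousness part is a corner case, and a fixed ranking loses one attribute, never both.
- **Investigators may code relatedness alike on both records.** The documents do not say how often they will. However, protocol 9.4.3.1 reserves Not Related for events readily explained by the underlying disease, so a worsening attributed to COPD after a Possible first phase is plausible.
- **SAEs get narratives (protocol 10.6.2) and a sponsor causality assessment (protocol 9.2), and all data are listed.** That keeps the information findable but does not correct the tables.

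A reader might infer more than the text supports:

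- *Every event that becomes serious loses something.* The SAP introduces linked records for severity changes only. That splits on seriousness are covered is inferred from its comparison of seriousness. If they are covered and severity is unchanged, the serious record is kept. If they are not, both records count.
- *AEs that stopped treatment disappear.* SAP 3.4.2 lists AEs leading to discontinuation without restricting them to TEAEs.
- *The SAE onset date biases an analysis.* No time-to-onset analysis of AEs is planned, and the first record keeps its own onset.

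**Conclusion.** The point holds, within limits. On its natural reading, Case 2 contradicts the SAP's own definition of treatment-emergent, can remove an event from the related-TEAE tables, and gives no answer when severity and seriousness conflict. It is a stated rule that can produce a wrong table, which goes beyond missing detail, so it should be changed.

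Overall TEAE incidence is safe, because one record of each pair is always kept. The documents do not say how many patients have pairs that differ in the attributes at issue, so no total understatement can be given. A reader might multiply the per-patient effect by an assumed count, but nothing in the documents supports any particular count. What can be said is that each affected patient lowers a related, serious or by-severity rate by about 2.5 points in the pooled active group, or 5.1 points in one dose group or pooled placebo. This assumes the planned allocation among the 59 dosed, and that the patient has no other event qualifying for the same table row.

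**What to change.** Rewrite SAP 3.4.2 Case 2 to derive one TEAE from each linked chain of post-dose records, with:

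- the earliest post-dose onset;
- the highest severity on any record;
- serious if any record is serious;
- related if any record is Related, Possible or missing.

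Working on the chain, not the pair, also covers the three-record sequence that protocol 9.4.3.5 allows (AE, then SAE, then non-serious AE). No ranking of severity against seriousness is then needed.

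The cost is one SAP paragraph and one programming step. The downside is slightly higher related and serious counts: an event may be tabulated as severe and related when its related record was the mild one. That is the cautious direction, and the listing still shows the individual records.

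No protocol or CRF change is needed. It would also come too late: a last dose on 29 April 2021 plus the 77 days from Day 85 to Day 162 ends follow-up in mid-July, before the SAP date of 26 August 2021.
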